### **Descriptive Measures**

Demographic variables, including age, education, income, insurance status, length of relationship, cancer type and treatments (survivor), medications and health habits will be measured at baseline by an in-house questionnaire and updated at subsequent visits. Clinical measures of weight and height will be made.

Presence of chronic medical conditions, used to characterize the health of the sample, will be measured by the Charlson Comorbidity Index,[85] a weighted index originally developed to predict mortality.

Shared activities at each time point will be measured using 2 items developed and used by this team. Survivors and spouses/partners are asked to rate engagement in a) leisure activities together and b) exercise activities together on a 0-4 scale, with a follow-up open-ended question about types of activities engaged in.

### **Process Measures**

Adherence. Adherence (% of prescribed sessions completed) will be tracked from attendance logs recorded by the exercise instructor to describe dose of exercise so that we can interpret and generalize our findings. Additionally, a single-item likert question will be asked of survivors and spouses/partners regarding how supportive they felt their partner was to them during the program and how supportive they felt they were to their partner.

Establishing the training effect and dose of exercise. Documenting the presence and degree of a training effect from experimental programs is an important element of any exercise training study[86]. In the absence of these measures it would be difficult to interpret unexpected, i.e., null, study findings. The improvements in fitness from exercise training are also an indicator of the dose of training, which can be used to interpret study outcomes. Evidence that the *Exercising Together* program effectively increased muscle strength will be evaluated by 1-repetition maximum testing for leg press and bench press. We have used the 1-RM technique in 6 studies of cancer survivors (age range: 35-89 y.o.) with no adverse events. The 1-RM test will be conducted according to established protocols[87]. Our in-house CV for this measure is 0.05-0.06. During periods of hospital recommendations for decreased in-person contact, the 1-repetition maximum testing for leg press and bench press will be substituted with a push-up test and plank test. These measures can be completed through video conferencing. To establish testing validity, these measures may also be completed in the testing lab when in-person contact resumes.

### **Additional Outcomes**

Physical activity (PA): To determine whether or not participation in *Exercising Together* changes overall PA levels and to compare our data against other studies that measure PA by self-report we will administer the 41-item Community Healthy Activities Model Program for Seniors (CHAMPS) PA questionnaire[88]. CHAMPS is a widely used and reliable[89] measure of PA in older adults that we've used in cancer survivors[38, 90-92].

Postural and dynamic stability will also be tested using the Mobility Lab ISWAY test and 6-min walk (APDM, Inc., <http://apdm.com>). The instrumented versions of the 6 min walk test and the Static Balance Test incorporate the use of wearable sensors to electronically detect changes in mobility beyond simple time measures or subjective scales. For each test, participants will wear six watch-sized movement sensors strapped to the wrists, ankles, chest, and waist using Velcro bands. The ISWAY consists of a 30-second trial of standing quietly and captures the amplitude, frequency, velocity and jerkiness of postural sway in multiple directions. This test will be completed once with the eyes open, feet together and once with the eyes closed, feet together. Postural sway is associated with balance control, is a strong predictor of falls, and is worse in those with neurological impairment.Mancini & Horak, 2010

Cancer-related loneliness: Participation in group-based exercise may facilitate development of friendships and comradery with others around a shared experience of cancer, which may result

in reduced feelings of loneliness. To assess changes in cancer-related loneliness, we will administer a validated cancer-related loneliness questionnaire, the Cancer Loneliness Scale Adams, 2017, to survivors. We will administer a modified version of the Cancer Loneliness Scale to spouses/partners in which language referring to the cancer survivor is revised to refer to the cancer survivor's intimate partner. We will administer the CLS and the modified CLS to newly enrolled participants.

**Intervention Feedback:** To better assess program feasibility and acceptability, as well as capture participant experiences not possible from our standardized surveys, we will be administering a survey (Post-Intervention Survey) at the end of the 6-month intervention that includes both qualitative and quantitative questions about the participant's experience in their assigned exercise program.

Study visits may be delivered in-person with additional precautions during periods of hospital recommendations for decreased in-person contact, and/or delivered remotely via video conferencing. In order to determine the validity of remote delivery, participants may be asked to complete both sets of testing at every time point (in-person plus remote). In such cases remuneration will be offered to offset the additional time asked of participants. If delivered remotely, select testing measures will be adapted to this type of delivery. These testing measures include:

1. Height (self-report collected if in-person assessment not expected)
2. Weight
3. Physical Performance Battery (PPB) (see 11. Objective physical function above, under Secondary Outcome Measures)
4. All surveys (see 1-5 above, under Primary Outcome Measures, and 12-17 under Secondary Outcome Measures and Other Pre-specified Outcome Measures) will continue to be sent out electronically as previously described. If a participant needs a paper survey to complete the survey, one will be provided or their data will be marked as "missed" if study staff are unable to mail a paper survey to the participant during their outlined testing window.

To assess upper body strength remotely, novel assessments to this trial will include:

5. Push-up test  
Measured by the number of push-ups completed in one continuous bout until fatigue
6. Plank test  
Measured by the amount of time in seconds that the participant is able to hold a plank position

The following measures will not be collected remotely:

1. DXA scan (see 6. Body composition above, under Secondary Outcome Measures)
2. Resting blood pressure and blood draw (see 7-10. Cardiovascular health/Inflammation above, under Secondary Outcome Measures)
3. Postural and dynamic stability (see Additional Outcomes above)
4. 1-repetition maximum testing for leg press and bench press (see process outcomes above)

Ancillary study: All study visits will be conducted remotely via videoconferencing. Measures will be collected in accordance with remote testing procedures described above.

#### **4.0 STUDY POPULATION**

For this study, we will recruit prostate, breast and colorectal cancer survivors and their co-residing spouse/partner, including both heterosexual intimate partners and same-sex couples.

We aim to recruit 294 couples (588 participants).

Ancillary study: We will recruit an additional 30 couples (60 participants) from five geographically underserved counties in Oregon (Wheeler, Malheur, Jefferson, Lake, and Benton counties).

#### **5.0 INCLUSION/EXCLUSION CRITERIA**

##### **Inclusion Criteria: *Survivors Only:***

- Histologically confirmed PC, BC or CRC without evidence of metastatic disease (confirmed by self-report on Health History Questionnaire. In the case a participant isn't able to confirm this criterion, a letter will be sent to his or her physician)
- Three years or less from diagnosis date, by month and year, at time of enrollment (confirmed by self-report on Health History Questionnaire. In the case a participant isn't able to confirm this criterion, a letter will be sent to his or her physician)
- Completed treatment (e.g., surgery, radiation and/or chemotherapy)  $\geq$ 6 weeks prior to enrollment. Concurrent adjuvant hormone therapy is permitted and must have been initiated  $\geq$  6 weeks prior to enrollment. For prostate cancer, Androgen Deprivation Therapy (ADT) may constitute primary treatment and must have been initiated  $\geq$  6 weeks prior to enrollment. For breast cancer, hormone therapy may constitute primary treatment and must have been initiated  $\geq$  6 weeks prior to enrollment. (confirmed by self-report on Health History Questionnaire. In the case a participant isn't able to confirm this criterion, a letter will be sent to his or her physician)
- Co-residing with an intimate partner or spouse who is willing to participate (confirmed by self-report on Health History Questionnaire)

##### **Inclusion Criteria: *Survivors and Spouses/Partners:***

- Age 35-80 years (confirmed by self-report on Health History Questionnaire)
- Underactive (< 2 strength training sessions per week, lasting 30 minutes or more per session, at a moderate intensity in the last month) (confirmed by self-report on Health History Questionnaire or by discretion of the Principal Investigator)

##### **Exclusion Criteria: *Survivors and Spouses/Partners:***

- Cognitive difficulties that preclude answering the survey questions, participating in the exercise classes or performance tests, or providing informed consent as determined by the professional opinion of the Principal Investigator, [name].
- A medical condition, movement or neurological disorder, or medication use that contraindicates participation in moderate intensity exercise. Specific contraindications include the following: declared pregnancy, poorly controlled diabetes, recent cardiac event, neuromuscular disease, untreated orthostatic hypertension, recent surgery, acute hernia, acute rheumatoid arthritis, severe memory disorders, severe balance disorder, inability to ambulate (use of an assistive device permitted), inability to stand for 3 minutes,

severe hearing or vision problem. (For Survivor: Confirmed by physician clearance; For Spouse/Partner: must answer 'No' to American College of Sports Medicine pre-participation screening questions [103]. If spouse/partner answers 'Yes' to either question they will be considered eligible upon physician clearance. Physician clearance may also be requested at the discretion of the Principal Investigator. For either: absence of pregnancy in persons who could possibly be pregnant but have not declared a pregnancy at screening, will be further screened with a pregnancy test administered at each testing visit, unless only participating remotely.)

- Knowingly unable to attend >75% of the intervention classes due to conflict with the designated time of day, days of the week, and/or location for the exercise class which they initially enrolled. (Confirmed by documentation in the Case Report Form titled "CRF - Participant Contact Info\_Exercising Together")
- Not fluent in English and therefore incapable of answering survey questions, participating in class, following directions during performance testing, and providing informed consent when English is the language used. (Confirmed by documentation in the Case Report Form titled "CRF - Participant Contact Info\_Exercising Together" or the professional opinion of the Principal Investigator, [name].)

Ancillary study: Participants recruited for the ancillary study will not be screened with a pregnancy test due to remote participation.

Ancillary study: To expand the pool of eligible participants, we will include survivors with a longer interval since diagnosis, as below.

Survivor only inclusion criterion:

- Ten years or less from diagnosis date, by month and year, at time of enrollment (confirmed by self-report on Health History Questionnaire. In the case a participant isn't able to confirm this criterion, a letter will be sent to his or her physician)

Ancillary study: Additional exclusion criteria:

- Insufficient internet connectivity to support videoconferencing (Confirmed by documentation in the Case Report Form titled "CRF - Participant Contact Info\_Exercising Together")

## **6.0 VULNERABLE POPULATIONS**

This study will not include any vulnerable populations. We will not collect any information about subjects' status as prisoners or pregnant women. Children will not be included because they do not get prostate, breast or colorectal cancer.

## **7.0 SETTING (REQUIRED)**

The primary study site will be Oregon Health & Science University (OHSU). Testing will be conducted at the OHSU Knight Cancer Research Building and the Oregon Clinical Translational Research Institute (OCTRI). Exercise training will be offered at OHSU and several community sites serving different geographic regions of the Willamette Valley, including an exercise site in Salem, OR, 60 miles south of Portland so that we can develop and test features of delivering the program outside of a large urban area. Study visits and exercise training may be delivered remotely via video conferencing. Conferences are set up by a private link sent to participants by

email. Any data recorded during training or study visits will be entered directly into databases on staff computers.

Ancillary study: For participants enrolled in the ancillary study, study visits and exercise training will be delivered remotely via video conferencing.

## **8.0 STUDY PROCEDURES AND SCHEDULE OF EVENTS**

### **Screening tests and procedures:**

Some potential participants will be sent a MyChart recruitment invitation via an email notification, as below, with the Subject “New Research Study” instructing them to log into MyChart to learn more and respond. The text of this invitation and a description of the MyChart recruitment process is contained in *Recruitment - EPIC MyChart procedures\_20191210*. The link in the MyChart invitation will take the potential participant to their MyChart homepage with a link to a description of the study. The text for the study summary is contained in *Recruitment - EPIC MyChart patient facing text\_20191210*. Potential participants will express interest or decline by pressing the associated buttons in MyChart, or they will not respond. If the potential participant indicates interest, they are automatically associated to the study in Epic with a status of “interested;” the study remains listed on the patient’s Research Studies page in MyChart, and the study team immediately receives an in basket notification in Epic so that they can follow up with the patient. If the patient clicks “No, Thank You” this study will no longer appear on their Research Studies page in MyChart, and the patient is automatically associated to the study in Epic with a status of “declined.” The recruitment script for contacting potential participants that express interest in the study is contained in the document *Screening - Phone Screen\_Survivor\_revised 20190212*.

Interested participants will be screened either by phone or in person using an IRB approved screening script. After initial screening, interested and eligible couples will come to the OHSU Knight Cancer Research Building and will be presented with an online IRB-approved Consent Form prior to any study-related procedure. The Consent Form will describe the goals of the study, study procedures, confidentiality, risks, benefits, and voluntary nature of the research. After participants view the consent online, and click the box that they have read and agree to participate (indicating that they have signed the consent), they will be sent links and requested to complete REDCap surveys. For the baseline testing session, couples will be asked to provide a fasting blood draw (which may be completed at an appointment separate of the baseline consenting visit but prior to initiation of the intervention), blood pressure, DXA scan, physical tests (PPB, 1RM leg and bench press, standing balance, and 6 minute walk test), and questionnaires. The testing session will take ~2-3 hours per couple, initially, and will be repeated at 3, 6, & 12 months and only take 1-2 hours. Following baseline testing, the Project Director will provide each couple with an envelope that contains their random assignment to a study group in order to retain blinding of the research assistants who conduct testing. Couples will be randomly assigned to 1 of 3 groups: 1) *Exercising Together*, 2) *Separate survivor / spouse/partner group exercise* 3) *Separate survivor / spouse/partner home exercise*. Enrollment will be stratified by cancer type and average couple age (<60 vs. 60-80). Assignment will be in random blocks of 6-9 couples for even enrollment.

During periods of hospital recommendations for decreased in-person contact, re-consent for the modified procedures will be done over the phone or via teleconference. Study team members will inform the participants of the modified procedures and note their verbal agreement to continue on the study.

Individuals who have not previously consented will be screened by phone or teleconference using an IRB approved screening script. After initial screening, interested and eligible couples will

consent by an electronic consent process setup through OCTRI's REDCap system (See 17.0 for a description of REDCap's Privacy, Confidentiality, and Data Security). A waiver of documentation of consent will be used to waive the need for a legally valid signature, however, an electronic signature and affirmation of consent will be collected in REDCap. Study staff will sign an attestation form in REDCap after the participant consents. Study staff will proceed with following the outline for remote testing procedures, as previously described in section 3.0 Study Design/Methodology.

**Ancillary study:** Individuals being recruited for the ancillary study will be screened by phone or videoconference using an IRB approved screening script, including screening questions about their internet connectivity and computer hardware for remote study participation. In order to assess participants' ability to participate in videoconferencing, they may be asked to facilitate gathering information about their internet speed from their internet service provider. After initial screening, interested and eligible couples will consent by an electronic consent process setup through OCTRI's REDCap system (See 17.0 for a description of REDCap's Privacy, Confidentiality, and Data Security). A waiver of documentation of consent will be used to waive the need for a legally valid signature, however, an electronic signature and affirmation of consent will be collected in REDCap. Study staff will sign an attestation form in REDCap after the participant consents. Study staff will proceed with following the outline for remote testing procedures, as previously described in section 3.0 Study Design/Methodology. If a participating couple is provided with an internet-capable device (i.e. Chromebook or tablet), they will sign a Device Agreement prior to receiving the device.

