**Survivor / Spouse/Partner Home Training:** Participants will be given equipment (vest, weights and/or resistance bands) and a program to do at home or a facility, depending on their preference. Within two weeks of randomization, each couple will have two one-hour training sessions with an exercise trainer who will teach them our functional strength training program, modified to their abilities and for home or facility use. We will also provide them with a general DVD of the strength program to follow at home. The trainer will check in weekly by phone in month 1 and monthly thereafter to assess tolerance and modify programs as needed. We have delivered home-based resistance training this way in our prior studies without any related injuries [42-44]. Participants can perform the program on days (allowing for 48 hours between sessions) and at times convenient for them. There is no requirement that partners exercise at the same time, though we will track the degree to which couples may do so in case we need to account for this in analyses.

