### **Measures and Data Collection**

Outcomes data will be collected at 0 (baseline, just prior to randomization), 3 (mid-intervention), 6 (post-intervention), and 12 months (6 mos. after completion of the intervention (follow-up)). Written surveys are completed on a computer at the testing facility at baseline and online for follow-up visits. All measures are completed by both members of the couple at each wave.

Primary Outcome Measure:

1. Dyadic coping

Measured by the Relationship Focused Coping Scale to assess the degree with which couples practice active engagement and protective buffering using questions on a scale from 1 (never) to 5 (very often).

[Time Frame: 0 baseline (just prior to randomization), 3, 6, and 12 months]

2. Emotional intimacy

Measured by the Dyadic Adjustment Scale (DAS) to assess each partner's satisfaction with their relationship by answering questions on a 6-point scale ranging from 1(always agree) to 6 (always disagree).

[Time Frame: 0 baseline (just prior to randomization), 3, 6, and 12 months]

3. Physical intimacy

Measured by the Physical Intimacy Behavior scale which asks participants the frequency that they engage in, initiate, and avoid intimate behaviors using questions on a scale from 1 (none of the time) to 4 (most or all of the time).

[Time Frame: 0 baseline (just prior to randomization), 3, 6, and 12 months]

4. Concealment of symptoms

Measured by the Emotional-Intimacy Disruptive Behavior Scale. Patients report the extent to which they engage in 8 behaviors using a scale from 1 (rarely or none of the time) to 4 (most or all of the time).

[Time Frame: 0 baseline (just prior to randomization), 3, 6, and 12 months]

5. Symptom incongruence

Measured by the degree of agreement between the survivor and spouse/partner ratings of the survivor's pain, fatigue and physical function in the past week using the following instruments: the Brief Pain Inventory (BPI) to measure pain intensity and pain interference, Functional Assessment in Chronic Illness Therapy (FACIT) fatigue survey to measure fatigue, and perceived physical function using a subscale of the SF-36 medical outcomes survey (all described below).

[Time Frame: 0 baseline (just prior to randomization), 3, 6, and 12 months]

Secondary Outcome Measure:

6. Body composition

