Measured by bone-free lean and fat mass (kg) for the whole body determined from a whole body dual energy x-ray absorptiometry (DXA) (Hologic-QDR Discovery Wi; APEX software, v.4.02) scan and used to calculate the % body fat.

[Time Frame: 0 baseline (just prior to randomization), 3, 6, and 12 months]

7. Cardiovascular health: serum fasting lipids

Measured by serum fasting lipids (total, high-density and low-density lipoprotein cholesterol and triglycerides)

[Time Frame: 0 baseline (just prior to randomization), 3, 6, and 12 months]

8. Cardiovascular health: insulin resistance

Measured by Homeostasis Model Assessment – Insulin Resistance - HOMA-IR: as the product of glucose and insulin, obtained from a fasting blood sample, divided by a constant.

[Time Frame: 0 baseline (just prior to randomization), 3, 6, and 12 months]

9. Cardiovascular health: resting blood pressure

Measured by the average of three consecutive resting blood pressure measurements (systolic and diastolic pressures).

[Time Frame: 0 baseline (just prior to randomization), 3, 6, and 12 months]

10. Inflammation

Measured by serum levels of high sensitivity C-reactive protein (hsCRP) and tumor necrosis factor alpha (TNF alpha) obtained from a fasting blood sample.

[Time Frame: 0 baseline (just prior to randomization), 3, 6, and 12 months]

11. Objective physical function

Measured by the Physical Performance Battery (PPB) to determine a person's ability to perform daily tasks independently. The PPB consists of 3 timed tests: 5 repeated chair stands, standing balance, and gait speed over 4 meters. Each test is scored 0 (unable) to 4 (completes without difficulty), based on quartiles of performance, then scores are summed. The possible range of scores is 0-12.

[Time Frame: 0 baseline (just prior to randomization), 3, 6, and 12 months]

12. Quality of life (QOL): QLQ-C30 and SF36

Measures QOL in cancer patients including subscales of physical and mental functioning. The SF-36 Health Survey assesses QOL in the general population.

[Time Frame: 0 baseline (just prior to randomization), 3, 6, and 12 months]

13. Depressive symptoms

Measured by the Center for Epidemiological Studies-Depression (CES-D) scale to determine the degree of depressive symptoms.

[Time Frame: 0 baseline (just prior to randomization), 3, 6, and 12 months]

14. Anxiety

Measured by the PROMIS anxiety short form using questions on a scale ranging from 1 (never) to 5 (always).

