of identifying eligible patients and from this point forward is no longer involved in the research. Our team will then send an information letter about the study to listed physicians for identified persons in the registry, notifying the physician that their patient will be sent information about the study. Physicians who determine that their patients should not receive study information are asked to return a form to the study investigator within a 3-week period. These persons will no longer be considered eligible to receive study information. All other potential participants will be sent an information letter briefly describing the study along with a response form and contact information of the research team. Persons who are interested in receiving more information about the study are asked to either contact our team directly (phone, email, text) or complete the response form and return it to our team. For all response forms returned to our team and in response to all other forms of inquiry, a member of the research staff will then contact interested persons to provide more study information to them and to screen for eligibility if they indicate a willingness to participate.

Potential participants will also be recruited via a study information mailing through the OHSU Cancer Registry and interested participants will contact us if they would like to learn more about the study and to check for eligibility. In addition we will recruit at community events, such as patient conferences and fundraisers, through study advertisements placed through various media outlets (i.e., internet, newspaper, radio), and by referral from the OHSU Prostate Cancer Clinic.

Ancillary study: Participants may also be recruited through the Oregon Office of Rural Health or the Oregon Rural Practice-based Research Network.

Members of the research team, will consult on eligibility issues as needed during recruitment. Eligible persons will come to the OHSU Knight Cancer Research Building to be consented and undergo baseline measures. Participants will also visit the OHSU Oregon Clinical Translational Institute for a blood draw collection at each measurement point.

Ancillary study: Participants in the ancillary study will participate remotely and will not visit OHSU.

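### The deadline for a separately booked baseline blood draw conflicts with the rule that baseline precedes randomisation, and read as an exception it lets three secondary outcomes be sampled after couples know their arm

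*Combined protocol and SAP*

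**What the plan says.** Three statements in the combined protocol and SAP bear on when the baseline blood sample is taken.

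- **General rule (section 3.0, Measures and Data Collection).** "Outcomes data will be collected at 0 (baseline, just prior to randomization), 3 (mid-intervention), 6 (post-intervention), and 12 months". The entries for lipids, HOMA-IR and inflammation each repeat it: "Time Frame: 0 baseline (just prior to randomization), 3, 6, and 12 months".
- **Order of procedures (section 8.0, Screening tests and procedures).** The draw is listed as part of baseline testing: "For the baseline testing session, couples will be asked to provide a fasting blood draw". Allocation is disclosed afterwards: "Following baseline testing, the Project Director will provide each couple with an envelope that contains their random assignment to a study group".
- **Provision for a separate draw (same paragraph of section 8.0).** The draw is one "which may be completed at an appointment separate of the baseline consenting visit but prior to initiation of the intervention".

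Two further statements show how the provision would work in practice. Blood is taken at a different place from the consent and baseline visit (section 10.0, Recruitment and Informed Consent): "Participants will also visit the OHSU Oregon Clinical Translational Institute for a blood draw collection at each measurement point". For the home arm (section 3.0, Study Arms), "Within two weeks of randomization, each couple will have two one-hour training sessions with an exercise trainer". No maximum interval from randomisation to first class is stated for the two supervised arms.

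**The concern.** A sample counts as a baseline value in a randomised comparison because it cannot depend on the allocation. The provision for a separate draw sets its limit at the start of training. That point comes after randomisation and after the couple has opened the envelope, so a draw that meets the stated deadline can still come too late.

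Participants are not blinded once they have the envelope. Between learning their arm and giving blood they could change diet or activity, or fail to attend because the assignment disappointed them. Baseline values or baseline missingness could then differ by arm for lipids, insulin resistance and inflammation. These are laboratory assays, so assessor bias is not a likely route.

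The permitted window may also differ by arm. Home couples have training sessions within two weeks of randomisation. Supervised couples start with their recruitment wave, and no maximum wait is given.

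**Working it through.** The plan gives no figure to reproduce. The check is a comparison of the statements, followed by the effect of a baseline shift on the planned model.

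**Step 1: order of events.**

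| Source | Latest point for the baseline draw |
|---|---|
| Section 3.0, general rule and each blood outcome | Before randomisation |
| Section 8.0, envelope sentence, with the draw counted as baseline testing | Before the envelope |
| Section 8.0, provision for a separate draw | Before the intervention starts |

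The first two rows agree. The third is later, because training follows randomisation. A draw made after the envelope but before the first session satisfies the third row and breaks the other two. If every draw had to come before the envelope, the third limit would never bind. It has a function only if a later draw is acceptable. No sentence says which rule prevails, or that the envelope waits for a separate draw.

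**Step 2: is a separate draw realistic?** Yes. The site differs, the draw needs 12 hours of fasting and abstention (section 8.0, Follow up tests and procedures), and it is paid as its own activity at $40 per couple (section 3.0, Participant Incentives).

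**Step 3: outcomes affected.** The secondary outcomes are items 6 to 15 in section 3.0, which makes ten. Those measured from blood are items 7 (lipids), 8 (HOMA-IR) and 10 (inflammation), which makes three. The primary outcomes, items 1 to 5, are questionnaires and fall outside the provision.

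**Step 4: passage of a baseline shift into the effect.** Under section 13.0 (Analysis Plan), Aim 2 uses the Aim 1 growth model, with baseline as intercept and the treatment effect as the group coefficient on the slope. Let δ be a between-arm shift in the baseline mean caused by sampling after allocation.

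- Visits: 0, 3, 6, 12 months. Mean = 21/4 = 5.25.
- Sum of squared deviations: 27.5625 + 5.0625 + 0.5625 + 45.5625 = 78.75.
- Change in the least-squares slope: −5.25δ/78.75 = −0.0667δ per month.
- Fitted change over 6 months: 6 × (−0.0667δ) = −0.4δ.
- Fitted change over 12 months: 12 × (−0.0667δ) = −0.8δ.

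Aim 3 also estimates the baseline-to-6-month period separately. If that is a straight line through 0, 3 and 6 months (mean 3, sum of squares 9 + 0 + 9 = 18), the slope changes by −3δ/18 per month and the 6-month change by −δ, so the whole shift passes through.

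These results assume complete data and a linear fit. A quadratic fit or missing visits would change the fractions.

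**Step 5: size of δ.** If a proportion p of one arm is drawn after allocation and the marker moves by s standard deviations in those people, δ = p × s. The documents give neither p nor s, so δ cannot be estimated from them.

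**The case against.** The strongest reply is that the plan already contains the right rule. Section 3.0 requires baseline before randomisation for each of these outcomes. Section 8.0 lists the draw as baseline testing and puts the envelope afterwards. On this view the provision only separates the draw from the consent visit for logistical reasons, the start of training is an outer limit, and all three statements can be met together.

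Part of this stands. A reader might infer that the draw is required only before training and that the plan sets no pre-allocation rule for it. The documents do not support that, because the rule is stated in section 3.0 and implied by the order in section 8.0. But the reply does not remove the conflict. Staff who book draws will work from the procedure section, where the only deadline specific to a separate draw is the later one, and nothing ties the envelope to that draw.

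A second reply is that the mechanism is weak. All three arms are prescribed the same basic strength programme for the same time, so there is little reason for fasting markers to move differently before training. The draw also carries a larger payment than any other test or survey. This stands, and it is why any bias is probably small.

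A third reply is that the analysis softens the effect: it uses growth models over four visits, and couples without a baseline sample stay in under maximum likelihood. This stands in part. The slope carries less than the full shift in the four-visit linear fit, but 80% of it at 12 months is not negligible. Missing draws that depend only on arm are handled when arm is in the model. Draws missed for reasons also tied to the unobserved marker are not.

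**Conclusion.** The concern holds as an internal inconsistency with a limited consequence. The deadline for a separate draw conflicts with the plan's own definition of baseline and with the position of the envelope. Read as a specific exception, it permits post-allocation baseline samples for lipids, HOMA-IR and inflammation.

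The reach is three of ten secondary outcomes and no primary outcome. The size is unknown: the share of separate draws, the share taken after allocation and any shift in the markers are not in the documents. A reader might go further and infer that the Aim 2 blood results are biased. That is not supported, since nothing shows that any draw has followed allocation or that the arms would move apart before training. The carry-over fractions of 0.4 at 6 months and 0.8 at 12 rest on a linear fit to four complete visits. They show how a shift would pass through, not that there is one.

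The change is worth making because it is cheap and removes a route to bias. It is not a serious threat to the trial.

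**What to change.** In section 8.0, change the deadline for a separately booked draw from the start of the intervention to *before the allocation envelope is given*. Add that the Project Director releases the envelope only once the draw is done or recorded as declined, with a matching item on the baseline checklist. Section 8.0 then agrees with section 3.0.

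If any baseline draws have already followed allocation:

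- record the draw date and the envelope date for each participant;
- flag the samples taken after the envelope;
- repeat the Aim 2 analyses of lipids, HOMA-IR and inflammation without those baseline values, as a sensitivity analysis.

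The cost is one sentence and one checklist item. The real downside is that allocation may be delayed for couples waiting for a blood appointment. Supervised classes are formed by wave, so the draw must be booked early enough that the delay does not hold up class formation.
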